Methadone is an opioid with one of the longest elimination half-life and has been used as an effective analgesic for acute, chronic, neuropathic, and cancer pain in adults, children, and even neonates¹⁻⁵. Its long duration of action and antagonism to the N-methyl-d-aspartate receptor may decrease the need for PCA use in the postoperative period. Gourlay² demonstrated the effectiveness and utility of perioperative methadone including the advantages of longer analgesia with no serious side effects of respiratory depression. A recent study by Gottschalk² in adult patients demonstrated a 50% reduction of postoperative opioids at 48 hours and lower pain scores after a single bolus of methadone before surgical incision. However, a major weakness of the study is that patients did not receive equipotent intraoperative opioids. In addition, the adolescent patient population will undergo a much larger surgical incision with potential for greater postoperative pain. Despite this potential benefit, methadone is seldom used in the perioperative setting. A more recent pharmacokinetic study of methadone in adolescents undergoing spine surgery failed to show a reduction in opioid consumption as it was powered to determine pharmacokinetics and not a secondary endpoint of postoperative opioid consumption. An appropriately powered study is still required to determine the efficacy of methadone in reducing postoperative pain after spine surgery.

1. Nicholson AB. Methadone for cancer pain. *Cochrane Database Syst Rev* 2007:CD003971 2. Gourlay GK et al. Pharmacodynamics and pharmacokinetics of methadone during perioperative period. *Anesthesiology* 1982; 57:458-67. 3. Gottschalk A et al. Intraoperative methadone improves postoperative pain control in patients undergoing complex spine surgery. *Anesth Analg* 2011; 112:218-23. 4. Sharma A, Tallchief D, Blood J, Kim T, London A, Kharasch ED: Perioperative pharmacokinetics of methadone in adolescents. *Anesthesiology* 2011; 115:1153-61. 5. Berde CB, Beyer JE, Bournaki MC, Levin CR, Sethna NF: Comparison of morphine and methadone for prevention of postoperative pain in 3- to 7-year-old children. *J Pediatr* 1991; 119:136-41

Section D: Purpose and Objectives

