Postoperatively, patients will be asked to rate their pain using a validated pain scale (a verbal rating scale where 0 = no pain and 10 = worse pain ever) by a blinded research staff member. These pain scores will be collected at 1 hour after entry into recovery and every 4 hours during the first five days of hospitalization both at rest and during activity by the nurses. The cumulative intravenous opioid requirement at 24, 48, and 72 hour will be recorded. The cumulative breakthrough intravenous opioid requirement after initiation of oral pain medication will also be collected. The level of sedation will be determined using the University of Michigan Sedation Scale. In addition, complications such as the incidence of hypotension (defined as mean arterial blood pressure less than 50 mm Hg), the need for vasopressors, the incidence of respiratory depression (defined as a respiratory rate less than 8 breaths per minute, respiratory arrest, or the need for naloxone), the incidence of hypoxemia or desaturation (defined as oxygen saturation [Sao₂] less than 90% or the need for a supplemental oxygen to maintain Sao₂ greater than 94%), the incidence of cardiac arrhythmias, and the incidence of nausea and vomiting including the treatment of side effects will be also recorded. Upon discharge from the hospital, the patients will be asked to keep a diary consisting of daily opioid usage, episodes of nausea and vomiting, daily activity level, and satisfaction scores. As part of standard routine post-surgical followup in the orthopedic clinic, information is collected from the patients which consist of questionnaires regarding pain scores, functional status, activity level, and quality of life. The research team will collect this information at 3 months and 6 months postoperatively.

Section G: Sample Size/Data Analysis**G1. Sample Size**

How many subjects (or specimens, or charts) will be used in this study?

Local: 98

Worldwide: 98

Please indicate why you chose the sample size proposed:

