The primary endpoint of the study is the morphine consumption during the first 72 postoperative hours. The secondary outcomes include pain scores and the incidence of side effects such as respiratory depression, nausea, and vomiting. Continuous data including pain scores will be first examined for a normal distribution by the Shapiro χ Wilk test. The outcome variables between the two groups will be compared with Student's t -test where appropriate, for normally distributed continuous data or by nonparametric tests if the data were not normally distributed. It is anticipated that the distribution of pain scores will not be normal and that non-parametric tests will be required. Categorical data including patient gender, ASA physical status, incidence of side effects (respiratory depression, need for oxygen beyond the first 2 hours, nausea and vomiting) will be compared by Fisher's exact test. Analysis of variance for repeated measures will be performed to compare differences in pain scores between the treatment groups with time. Data will be presented as mean, standard deviation, median values or numbers (percentages). P values less than 0.05 will be considered statistically significant. In order to maintain a robust statistical analysis, we will also examine the differences in subjects with and without completely evaluable data in known factors that affect postoperative pain after spine surgery (e.g., age, gender, ASA physical status, duration of surgery, intraoperative opioids medications, time of the PACU stay, mean and peak pain scores and recorded opioid consumption in the PACU before discharge). Failure to show a difference in these factors may suggest that the missing data can be considered to be missing at random.

Section H: Potential Risks/Discomforts

H1. Potential Risks/Discomforts

Describe and assess any potential risks/discomforts; (physical, psychological, social, legal, or other) and assess the likelihood and seriousness of such risks:

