In this study, we are comparing the addition of another opioid pain medication to reduce pain scores and overall total hospital opioid consumption. Current standard practices for patients undergoing multi-level spine surgery will be used with the exception of methadone given to the treatment group. Methadone may induce prolongation of the rate-corrected QT interval (QTc); however, patients with cardiac arrhythmias or congenital heart disease will be excluded from the study. Side effects of respiratory depression from methadone should not be greater than with typical morphine usage.

Additional risks of the study are the small chance of loss of privacy. The data will be coded. No data identifying the patient will be extracted from the medical records and all data will be kept locked in the offices of the Principal Investigator. Any electronic version will be kept in a password protected network servers controlled by the IT services at the TCH. Computers with access to this network are kept in a locked office where entry is limited to those with an ID key card. This office is located inside the office of the Department of Anesthesiology at Texas Children's Hospital. Unauthorized individuals would not be able to enter these facilities. The likelihood of such events is minimal.

H2. Data and safety monitoring plan

Do the study activities impart greater than minimal risk to subjects?

Yes

NOTE: The answer to the questions in H2 requires the completion of the form: 'Section H – Data and Safety Monitoring Plan' as an attachment in Section S.

H3. Coordination of information among sites for multi-site research

Is the BCM Principal Investigator acting as the SPONSOR-INVESTIGATOR for this multi-site research?

No or Not Applicable

Is BCM the COORDINATING CENTER for this multi-site research?

No or Not Applicable

Section I: Potential Benefits

Describe potential benefit(s) to be gained by the individual subject as a result of participating in the planned work.

Patients assigned to the methadone group may have reduced postoperative pain scores and a reduction of total consumption of postoperative opioids. Patients with less opioid use may benefit from fewer side effects. However, it is possible that there will be no benefits from participating in the study.

Describe potential benefit(s) to society of the planned work.

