Data from this study can be used to determine if methadone provides better pain control in the perioperative setting. Knowledge obtained from this study may allow anesthesiologists from other institutions caring for children and adolescents undergoing similar painful procedures to use this medication to reduce pain.

Do anticipated benefits outweigh potential risks? Discuss the risk-to-benefit ratio.

The risks in this study do not vary from the risks of standard practices at TCH for children undergoing multi-level thoracolumbar spinal instrumentation and fusion. The additional minor risk of an unlikely loss of privacy is outweighed by the societal benefits from this knowledge.

Section J: Consent Procedures

J1. Waiver of Consent

Will any portion of this research require a waiver of consent and authorization?

No

J1a. Waiver of requirement for written documentation of Consent

Will this research require a waiver of the requirement for written documentation of informed consent?

No

J2. Consent Procedures

Who will recruit subjects for this study?

PI
PI's staff

Describe how research population will be identified, recruitment procedures, any waiting period between informing the prospective participant and obtaining consent, steps taken to minimize the possibility of coercion or undue influence and consent procedures in detail.

Patients presenting for spinal surgery will be identified from the Texas Children's Hospital operating room schedule that is routinely available to pediatric anesthesiologists. This will be cross referenced with the pediatric orthopedic surgeons' operative schedule as these cases are scheduled weeks to months in advance. The chart is reviewed to insure that the patient qualifies based on the inclusion and exclusion criteria. The study staff will ask the surgeon if they may approach the patient and parents about the study.

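### Respiratory depression is to be compared by a Fisher p-value with no effect estimate or interval, which at 28 to 49 per arm cannot support the expectation that risk is not greater

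*Combined protocol and SAP*

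**What the plan says.** **The expectation.** H1 describes the study as adding another opioid. It names QTc prolongation as a possible effect of methadone and then says "Side effects of respiratory depression from methadone should not be greater than with typical morphine usage". It gives no rate, margin or tolerable excess. The risk-to-benefit answer in Section I says "The risks in this study do not vary from the risks of standard practices at TCH". E1 classes the research as greater than minimal risk, and H2 answers yes to the same question.

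**The design.** Under F2, both arms receive the same sufentanil range and the same morphine PCA. The treatment arm also receives methadone.

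**The outcome.** F2 records "the incidence of respiratory depression (defined as a respiratory rate less than 8 breaths per minute, respiratory arrest, or the need for naloxone"). G2 states: "The secondary outcomes include pain scores and the incidence of side effects such as respiratory depression, nausea, and vomiting".

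**The analysis.** G2 lists the side effects to be tested: respiratory depression, need for oxygen beyond two hours, and "nausea and vomiting) will be compared by Fisher's exact test". It adds that "P values less than 0.05 will be considered statistically significant", and on presentation that "Data will be presented as mean, standard deviation, median values or numbers (percentages"). No risk difference, confidence interval, non-inferiority margin or safety power statement appears. G1 sizes the trial on opioid use alone.

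**The concern.** Methadone is given on top of the opioids that both arms receive, so whether it adds respiratory depression is a question readers will bring to the results. The plan would answer it with two percentages and a p-value. When events are few and arms are small, a p-value above 0.05 is likely whether or not there is a moderate excess, and it does not show how large an excess the data still allow.

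Participants are aged 10 to 17, and Section I expects the results to inform use at other institutions. If the report says only that the arms did not differ significantly, a reader cannot tell an informative null from an uninformative one.

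**Working it through.** **Inputs.** G1 gives 28 evaluable and 49 recruited per group. F1 instead says 56 patients in all, which is 28 per group. Allocation is 1:1 (F1). The test is Fisher's exact at 0.05 (G2); sidedness is not stated, so two-sided is taken first.

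**The plan's own figure.** There is none for respiratory depression. For opioid use, G1's inputs (difference 75 mg, SD 75 mg, 80% power) give n = 2 × (1.96 + 0.84)² × 75²/75² ≈ 15.7. That is 16 per group, or 17 by the t-test, and not 28. A 50% loss would need 28/(1 − 0.5) = 56 per group, not 49. These are separate matters. They do not affect this point because both 28 and 49 are carried through below.

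**Step 1: what the test needs.** For k events against 0 with n per arm, the two-sided p-value is 2 × C(n,k)/C(2n,k).

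- n = 28, k = 5: 2 × 98,280/3,819,816 = 0.0515
- n = 28, k = 6: 2 × 376,740/32,468,436 = 0.023
- n = 49, k = 5: 2 × 1,906,884/67,910,864 = 0.056
- n = 49, k = 6: 2 × 13,983,816/1,052,618,392 = 0.027

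So 6 against 0 is the threshold at both sizes. That is 6/28 = 21.4% or 6/49 = 12.2%, against none. With one control event, 7 against 1 gives 0.051 (n = 28) and 0.059 (n = 49), while 8 against 1 gives 0.025 and 0.031. A one-sided test at 0.05 would need 5 against 0 (p = 0.026 and 0.028).

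**Step 2: power to declare an excess.** Power is the sum, over all tables with two-sided p<0.05 and more methadone events than control events, of the product of the two binomial probabilities. All rates are assumed.

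| Control v methadone | n = 28 | n = 49 |
|---|---|---|
| 5% v 15% | 8% | 24% |
| 10% v 20% | 8% | 19% |
| 5% v 20% | 21% | 49.5% |
| 10% v 30% | 33% | 63% |
| 5% v 30% | 58% | 89% |

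**Step 3: what an interval adds.** The Newcombe interval runs from d − √[(p₁ − l₁)² + (u₀ − p₀)²] to d + √[(u₁ − p₁)² + (p₀ − l₀)²]. Here d = p₁ − p₀, subscript 1 is methadone, and l and u are each arm's Wilson limits.

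- 4/28 v 1/28: d = 0.143 − 0.036 = 0.107. The Wilson limits are 0.057 to 0.315 and 0.006 to 0.177. Lower: 0.107 − √(0.086² + 0.141²) = −0.058. Upper: 0.107 + √(0.172² + 0.029²) = 0.282. The excess is 10.7 points, 95% CI −5.8 to +28.2.
- 5/28 v 0/28: d = 0.179, 95% CI +2.2 to +35.6 points, although Fisher's p is 0.0515.
- 0 v 0: 95% CI ±12.1 points at n = 28 and ±7.3 points at n = 49.

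Even a trial with no events would leave an excess of about 7 to 12 points within the interval. The p-value and percentages do not convey this.

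**The case against.** The H1 sentence is a risk description on an ethics form, worded as an expectation. It is not a hypothesis, and G2 does not link the Fisher test to it. A reader might infer that the investigators intend to treat a non-significant result as proof of equal safety, but no section says so. The nearest text is G2's remark on missing data, where failure to find differences may suggest missingness at random; that concerns other factors, not safety. Section C does not help this inference either. It explains that an earlier study "failed to show a reduction in opioid consumption as it was powered to determine pharmacokinetics and not a secondary endpoint", which accounts for a null result and does not criticise how it was read. If anything, it suggests that the investigators know the limits of an unpowered endpoint. This objection stands.

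A reader might also infer that even a large excess would pass as no difference. That is not generally true: at 49 per arm, power is 63% for 10% v 30% and 89% for 5% v 30%. The dropout allowance in G1 concerns incomplete data in a calculation built on opioid use, so respiratory events may be available for more than 28 per arm.

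Counts will be shown, so 5 against 0 would be visible. F2 also records sedation, hypoxemia and naloxone need. H2 refers to a separate Data and Safety Monitoring Plan form that was not among the documents reviewed, so nothing can be said about its content. Limited power for safety is common in a trial sized on efficacy.

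All of this narrows the point but does not remove it. Visible counts do not show what size of excess remains compatible with the data, and G2 plans nothing that does.

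**Conclusion.** The point holds as a reporting weakness in G2. The planned between-arm comparison of respiratory depression is a p-value with counts and percentages. It needs 6 events against 0, or 8 against 1, at both 28 and 49 per arm. Power is 8% to 24% for an assumed 5% v 15%, and 8% to 19% for an assumed 10% v 20%. A non-significant result therefore cannot by itself support the H1 expectation.

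The thresholds rest only on a two-sided Fisher test and the stated group sizes. The power figures also rest on event rates that the documents do not give. The primary comparison of opioid use is unaffected.

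Separately, Section I's statement that risks do not vary from standard practice does not fit the added opioid and QTc risk in H1 or the greater-than-minimal-risk answers in E1 and H2.

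**What to change.** In G2, report each safety outcome as events and patients per arm, with the risk difference and a 95% CI by a named method such as Newcombe. Keep Fisher's p-value as a supplement, and state that a non-significant p-value will not be taken as evidence of equal safety. Because the interval and the test can disagree near the boundary, as with 5 against 0 at 28 per arm, say in advance that the interval is the basis for interpretation.

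Reconcile the Section I statement with H1, E1 and H2. There is no need to declare the excess risk unknown: Section C cites perioperative methadone evidence on respiratory depression that cannot be assessed from these documents.

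The cost is a few sentences, with no new patients or data. The downside is that the intervals will be wide and the safety conclusion will look less favourable.
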